Appendix 8: EQ-5D-5L Scale

By placing a tick (✓) in one box in each group below, please indicate which statements best describe your own health state today.

Mobility

- I have no problems in walking about.
- I have slight problems in walking about.
- I have moderate problems in walking about.
- I have severe problems in walking about.
- I am unable to walk about.

Self-Care

- I have no problems caring for myself.
- I have slight problems washing or dressing myself.
- I have moderate problems washing or dressing myself.
- I have severe problems washing or dressing myself.
- I am unable to wash or dress myself.

Usual Activities (e.g. work, study, housework, family or leisure activities)

- I have no problems with performing my usual activities.
- I have slight problems performing my usual activities.
- I have moderate problems performing my usual activities.
- I have severe problems performing my usual activities.
- I am unable to perform my usual activities.

Pain/Discomfort

-
- I have no pain or discomfort.
- I have slight pain or discomfort.
- I have moderate pain or discomfort.
- I have severe pain or discomfort.
- I have extreme pain or discomfort.

Anxiety/Depression

- I am not anxious or depressed.
- I am slightly anxious or depressed.
- I am moderately anxious or depressed
- I am severely anxious or depressed
- I am extremely anxious or depressed

[figure not shown]
To help reflect your health status, we have drawn a scale (similar to a thermometer). On this scale, the best health status you can imagine is marked 100 and the worst health status you can imagine is marked 0.

Please mark your health status today on the scale on the right.

Please draw a line from the box to the point on the scale that indicates how good or bad your health status is today.

Your health status today

The best health status you can imagine

The worst health status you can imagine

Appendix 9: EORTC-QLQ-C30 (v3) Quality of Life Scale

We would like to know about you and your health status. Please answer all the questions yourself by circling the number that best applies to you. There are no "right" or "wrong" answers. The information that you provide will be kept confidential.

Please fill in your initials: _____

Date of Birth: _____ YYYY_____MM_____DD

Today's date: _____ YYYY_____MM_____DD

	Not at All	A Little	Quite a Bit	Very Muc h
1. Do you have any trouble doing strenuous activities, like carrying a heavy shopping bag or a suitcase?	1	2	3	4
2. Do you have any trouble taking a long walk?	1	2	3	4
3. Do you have any trouble taking a short walk outside of the house?	1	2	3	4
4. Do you need to stay in bed or a chair during the day?	1	2	3	4
5. Do you need help with eating, dressing, washing yourself or using the	1	2	3	4

During the past week:

	Not at All	A Little	Quite a Bit	Very Muc h
6. Were you limited in doing either your work or other daily activities?	1	2	3	4
7. Were you limited in pursuing your hobbies or other leisure time activities?	1	2	3	4
8. Were you short of breath?	1	2	3	4
9. Have you had pain?	1	2	3	4
10. Did you need to rest?	1	2	3	4
11. Have you had trouble sleeping?	1	2	3	4
12. Have you felt weak?	1	2	3	4
13. Have you lacked appetite?	1	2	3	4

14. Have you felt nauseated?	1	2	3	4
15. Have you vomited?	1	2	3	4
16. Have you been constipated?	1	2	3	4

During the past week:

	Not at All	A Little	Quite a Bit	Very Muc h
17. Have you had diarrhea?	1	2	3	4
18. Were you tired?	1	2	3	4
19. Did pain interfere with your daily activities?	1	2	3	4
20. Have you had difficulty in concentrating on things, like reading a	1	2	3	4
21. Did you feel tense?	1	2	3	4
22. Did you worry?	1	2	3	4
23. Did you feel irritable?	1	2	3	4
24. Did you feel depressed?	1	2	3	4
25. Have you had difficulty remembering things?	1	2	3	4
26. Has your physical condition or medical treatment interfered with your	1	2	3	4
27. Has your physical condition or medical treatment interfered with your	1	2	3	4
28. Has your physical condition or medical treatment caused you financial	1	2	3	4

For the following questions, please circle the number between 1 and 7 that best applies to you

29. How would you rate your overall health during the past week?

1 2 3 4 5 6 7

Very poor

Excellent

30. How would you rate your overall quality of life during the past week?

1	2	3	4	5	6	7
Very poor						Excellent

Summary of Amendment

Alternative Version 2 to Version 1 (Version Date:May.11, 2017)

Main change	Description
1. Sample sizes changed from minimum of 60 patients to 20-60 patients	When 28 patients were enrolled, several early PD were observed, and the Lugano 2014 criteria made response evaluation difficult due to the lack of a definition for pseudo-progression. Therefore, enrollment was paused, but treatment was continued to confirm the true nature of the pseudo-progression according to investigator's discretion. After 3 months of observation and in-depth analysis of the 28 patients, sintilimab demonstrated 67.9% ORR when taking pseudo-progression into consideration. Planned total enrollment was not reached. When hypothesizing that the 15 yet-to-be-enrolled patients would be non-responders, there would be 19 responders out of 43 (28 actually enrolled + 15 fictive), providing a 95% CI by Wilson's method of 30.4%-58.9%, where the lower boundary is still greater than the pre-planned 30% threshold. There's no need to enroll a total of 60 patients.
2. Add RNA expression as a biomarker	Detection of RNA expression could help to capture potential biomarker for predicting response.
3. Modify the treatment duration up to 24 months	No clinical benefit evidence to support a long treatment duration for more than 2 years.
4. Modify the final injection volume (after preparation) from 250 ml to 100 ml	Based on the updated stability test of sintilimab, the recommended final concentration is 1.5~2 mg/ml.
5. Remove the second interim analysis	There no need to perform a second interim analysis.

## STATISTICAL ANALYSIS PLAN

Innovent Biologics (Suzhou) Ltd  
Protocol number: CIBI308D201

Version: 2.0  
Version Date: 2020-02-28

---

### VERSION HISTORY

---

SAP Version	Approval date	Description of changes
1.0	2019-06-24	Update according to protocol amendment 2.0 and reorganized to new SAP template

## STATISTICAL ANALYSIS PLAN

Innovent Biologics (Suzhou) Ltd  
Protocol number: CIBI308D201

Version: 2.0  
Version Date: 2020-02-28

### ABBREVIATION

ADA	Anti-drug antibody
AE	Adverse event
BDRM	Blinded data review meeting
BMI	Body mass index
CI	Confidence interval
CR	Complete response
CSR	Clinical study report
CTCAE	Common Terminology Criteria for Adverse Events
DCR	Disease control rate
DMC	Data monitoring committee
DoR	Duration of response
ECG	Electrocardiography
ECOG PS	Eastern Cooperative Oncology Group Performance Status
eCRF	Electronic case report form
FAS	Full analysis set
GCP	Good clinical practice
ICH	International Council for Harmonisation of Technical Requirements for Pharmaceuticals for Human Use
irAE	Immune related adverse event
MedDRA	Medical Dictionary for Regulatory Activities
ORR	Objective response rate
PD	Disease progression
PFS	Progression free survival
PK	Pharmacokinetics
PP	Per protocol
PR	Partial response
SAE	Serious adverse event
SAP	Statistical analysis plan
SD	Stable disease
SS	Safety set
TEAE	Treatment emergent adverse event
TTR	Time to response

## 1 Introduction

This statistical analysis plan (SAP) is based on CIBI308D201 “A Multicenter, Single-arm, Phase II Clinical Trial Evaluating the Efficacy and Safety of IBI308 Monotherapy in the treatment of relapsed or Refractory Extranodal NK/T-Cell Lymphoma, Nasal Type (ORIENT-4)” protocol, version 2.0 on July 05, 2017 and China regulator guidances. The objective of this SAP is to provide detailed definition of the endpoints and planned statistical analyses.

### 1.1 STUDY OBJECTIVES

- Primary Objectives

To evaluate the objective response rate (ORR) of IBI308 monotherapy in the treatment of relapsed or refractory extranodal natural killer (NK)/T-Cell lymphoma, nasal type (ENKTL-NT).

- Secondary Objectives

- To evaluate the rate of complete response (CR) and partial response (PR) of IBI308 monotherapy in the treatment of relapsed or refractory ENKTL-NT;
- To evaluate the disease control rate (DCR) of IBI308 monotherapy in the treatment of relapsed or refractory ENKTL-NT;
- To evaluate the time to response (TTR) of IBI308 monotherapy in the treatment of relapsed or refractory ENKTL-NT;
- To evaluate the duration of response (DOR) of IBI308 monotherapy in the treatment of relapsed or refractory ENKTL-NT;
- To evaluate the progression-free survival (PFS) and 6-month PFS rate of IBI308 monotherapy in the treatment of relapsed or refractory ENKTL-NT;
- To evaluate the overall survival (OS) and 12-month OS rate of IBI308 monotherapy in the treatment of relapsed or refractory ENKTL-NT;
- To evaluate the safety of IBI308 monotherapy in the treatment of relapsed or refractory ENKTL-NT;
- To evaluate the quality of life of subjects with relapsed or refractory ENKTL-NT after IBI308 monotherapy, using EuroQoL 5 Dimensions 5 Levels (EQ-5D-5L) and European Organization for Research and Treatment of Cancer Quality-of-Life Questionnaire-Core 30 (EORTC QLQ-C30).

## 1.2 STUDY DESIGN

This is a multicenter, single-arm, phase II clinical trial evaluating the efficacy and safety of IBI308 monotherapy in the treatment of relapsed or refractory ENKTL-NT.

This study will enroll patients with relapsed or refractory ENKTL-NT to receive IBI308 200mg IV Q3W until progression disease (PD), death, intolerable toxicity, withdrawal of ICF, or other reasons stated in the protocol with a maximum treatment duration of 24 months. For subjects who experience PD for the first time and are clinically stable, the investigator can continue treatment until subsequent PD, death, intolerable toxicity, withdrawal of ICF, or other reasons stated in the protocol with a maximum treatment duration of 24 months.

The primary efficacy endpoint of this study is ORR defined as percentage of subjects with radiological CR or PR as best overall response. The primary endpoint is analyzed after last subjects completing up to 24 weeks followup. Lugano 2014 criteria will be used for ORR. After 24 weeks, IWG 2007 criteria will be used to assess responses.

Subjects will continue safety followup upto 90 days after last dose of study treatment.

## 1.3 SAMPLE SIZE

The hypothesis of this study is to evaluate the effectiveness of ORR based on Lugano 2014:

H0: ORR $\leq$ 30%

H1: ORR $>$ 30%

For the primary efficacy endpoint ORR, the point estimate and its (100- $\alpha$ )% confidence interval ( $\alpha$  maybe different from 5 if interim analysis is added) will be provided using binomial distribution. If the lower limit of the confidence interval is greater than 30%, the effectiveness of IBI308 is established for r/r ENKTL. This is a single-arm trial, and 20-60 subjects are planned to be enrolled for the study. Under the assumption of an ORR=50%, with 43 subjects, there is 80% power to reject H0 under a two-sided type I error rate of 0.05.

After first 20 subjects enrolled, a safety evaluation will be conducted before continuing enrollment.

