One interim analysis is planned for this study. It will be conducted after the first 20 subjects have completed the protocol-specified treatment to evaluate the safety.

Primary efficacy endpoint:

ORR and the corresponding $1-\alpha\%$ CI is estimated using binomial distribution to test for superiority.

Secondary efficacy endpoints:

TTR, DoR, PFS, and OS will be estimated through the median values and the corresponding 95% CIs using the Kaplan-Meier method. PFS and 6-month PFS curves will be plotted.

CR, PR, and DCR and the corresponding 95% CIs will be estimated using binomial distribution.

Safety analysis:

	
The incidence and severity of AEs will be summarized for each treatment arm, and the abnormal changes in laboratory measurements will be presented.
 
Immunogenicity analysis:
 
The positive rates of ADAs and NAbs will be summarized.
 
Quality of life analysis:
 
Data based on EQ-5D-5L and EORTC QLQ-C30 will be analyzed using descriptive statistics.
 
Biomarker analysis:
 
PD-L1 expression and number of TIL in tissue samples of subjects with relapsed or refractory ENKTL-NT, dynamic changes in EBV DNA copy number in plasma and peripheral blood lymphocytes, immune cell phenotyping, and association between immune-related cytokines and efficacy of anti-PD-1 treatment will be analyzed using descriptive statistics.

--	--

Table 1. Schedule of visits

Phase	Screening	Treatment						End-of-Treatment Visit ²²	Safety Follow-Up	Survival Follow-up ²³
		Cycle 1	Cycle 2	Cycle 3	Cycle 4	Cycle 5	Cycle 6–N			
Visit	1	2	3	4	5	6	7–N	Premature discontinuation/end-of-treatment visit		
Day	-28 to -1	Day 1	Day 22 (±3 days)	Day 43 (±3 days)	Day 64 (±3 days)	Day 85 (±3 days)	Q3W (±3 days)		90 days (±7 days) since the last dose	Q60D (±7 days) after safety follow-up
General Study Procedures										
Signed ICF ¹	X									
Inclusion/Exclusion Criteria	X									
Demographics/Medical History/Previous Medication ²	X									
Vital Signs ³	X	X	X	X	X	X	X	X	X	
Weight/Height ⁴	X							X		
Physical Examination	X		X	X	X	X	X	X		
ECOG PS Score	X	X	X	X	X	X	X	X		
12-Lead ECG ⁵	X			X		X	X	X		
Count of Whole Blood Cells/Blood Biochemistry/Routine Urinalysis ⁶	X		X	X	X	X	X	X	X	

Phase	Screening	Treatment						End-of-Treatment Visit ²²	Safety Follow-Up	Survival Follow-up ²³
		Cycle 1	Cycle 2	Cycle 3	Cycle 4	Cycle 5	Cycle 6–N			
Visit	1	2	3	4	5	6	7–N	Premature discontinuation/end-of-treatment visit		

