8.2 Hypothesis Test

The primary efficacy endpoint is ORR evaluated using the 2014 Lugano Criteria. The hypotheses for the superiority test are as follows:

$$H_0: \text{ORR} \leq 30\%$$

$$H_1: \text{ORR} > 30\%$$

The superiority is determined using confidence intervals (CIs). Superiority of IBI3088 monotherapy for the treatment of relapsed or refractory ENKTL-NT is established if the lower limit of the $(1-\alpha)\%$ CI for ORR is greater than 30% (α may be adjusted according to interim analysis).

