8.4.2 Analysis of primary efficacy endpoint

ORR is evaluated using the 2014 Lugano Criteria:

$$ORR = \frac{\text{Number of Subjects with CR + PR}}{\text{Total Number of Subjects}} * 100 \%$$

, superiority is tested using $(1-\alpha)\%$ CI

based on the binomial distribution.

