8.5 Sample size estimation

This is a single-arm trial. The primary objective is to evaluate the efficacy of IBI308 monotherapy for the treatment of relapsed or refractory extranodal NK/T-Cell Lymphoma. 20-60 subjects will be enrolled. Assuming a null hypothesis of 30% ORR, α of 0.05 (two-sided), power of 80%, a 50% ORR after IBI308 treatment will be achieved and the minimum sample size will thus be 43.

The sponsor will evaluate the safety data from the first 20 subjects to determine whether the study shall be discontinued prematurely due to safety concerns.

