### **5 Statistical Methods**

#### **5.1 GENERAL RULES**

All the statistical analyses will be performed with SAS 9.2 (or higher).

Unless otherwise stated, all TFLs will follow the rules below:

- Baseline value: last available data before first dose.
- Significant level and multiplicity adjustment: 5% two-sided level, no adjustment will be made.
- Summary statistics for continuous variables: N, mean, standard deviation, median, Q1, Q3, min and max.
- Categorical variables: number of subjects and percentage.
- Denominator in percentage calculation: unless otherwise specified, subjects with missing values will not be included. Number of subjects with missing value will be provided.

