### 5.5.1 Primary Analysis

The ORR is defined as the proportion of subjects with CR or PR as Best Overall Response (BOR).

$$ORR = \frac{CR + PR}{\text{Total Number of Subjects}} * 100\%$$

For ORR, the point estimate and 95% confidence interval will be provided using exact binomial distribution.

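### The 80% power stated for 43 subjects does not match the plan's own success rule: with the exact 95% interval, 20 of 43 responders are needed and power is 72.9%

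*SAP*

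**What the plan says.** **Power claim.** SAP 1.3, assuming a true ORR of 50% against a null of 30%, states that "with 43 subjects, there is 80% power to reject H0 under a two-sided type I error rate of 0.05". Protocol 8.5 uses the same inputs (30%, 50%, two-sided 0.05, 80%) and concludes that "the minimum sample size will thus be 43".

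**Success rule.** SAP 1.3: "If the lower limit of the confidence interval is greater than 30%, the effectiveness of IBI308 is established for r/r ENKTL". Protocol 8.2 has the same rule: "Superiority of IBI3088 monotherapy for the treatment of relapsed or refractory ENKTL-NT is established if the lower limit of the" interval for ORR is above 30%.

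**Level.** SAP 5.1 sets "5% two-sided level, no adjustment will be made". Protocol 8.4.11 leaves α unadjusted for the safety look at 20 subjects, and SAP 5.10 plans no interim analysis. The interval is therefore a 95% interval.

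**Type of interval.** SAP 5.5.1: "For ORR, the point estimate and 95% confidence interval will be provided using exact binomial distribution". This is the only place that specifies which binomial interval is used for the primary analysis. SAP 1.3 refers only to the binomial distribution. Protocol 8.4.2 says "based on the binomial distribution", and the synopsis says "CI is estimated using binomial distribution to test for superiority".

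**The concern.** The power statement, the decision rule and the interval sit in different sections, and no section checks them against each other. An exact binomial interval is wider than the approximations commonly used for sizing, so a sample size from an approximation can fall short once the exact interval makes the decision.

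The 80% at 43 subjects is the only operating characteristic the plan gives for its primary endpoint. If it is wrong under the plan's own rule, the stated risk of a false-negative trial is too low. Calling the interval only binomial in three places also leaves the method open. At 43 subjects that choice decides whether 19 responders counts as success.

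**Working it through.** **Inputs.** p0 = 0.30 and p1 = 0.50 (SAP 1.3, protocol 8.5); n = 43; two-sided α = 0.05 without adjustment (SAP 5.1); success if the lower 95% limit exceeds 0.30 (SAP 1.3, protocol 8.2); exact binomial interval (SAP 5.5.1), read as Clopper-Pearson.

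**1. Reproducing the plan's figure.** The documents name no method, so this is inferred. The one-sample normal approximation, with the null variance in the critical value, gives

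n = [(1.96·√0.21 + 0.8416·√0.25) / 0.20]² = 43.49

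Power at 43 = Φ[(0.20·√43 − 1.96·√0.21) / 0.50] = 79.6%

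This accounts for 43 and 80%.

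**2. Threshold under the exact interval.** The Clopper-Pearson lower limit L for x responders solves P(X ≥ x | n, L) = 0.025. So L exceeds 0.30 exactly when P(X ≥ x | n, 0.30) is below 0.025.

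| Responders of 43 | Exact lower 95% limit | P(X ≥ x) at ORR 30% | Result |
|---|---|---|---|
| 19 | 29.1% | 0.0342 | fails |
| 20 | 31.2% | 0.0164 | passes |

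**3. Power and error under that threshold.**

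- Power: P(X ≥ 20 | 43, 0.50) = 72.9%.
- False-negative risk: 100% − 72.9% = 27.1%, against the implied 20%.
- One-sided type I error: P(X ≥ 20 | 43, 0.30) = 1.6%.
- True ORR at which P(X ≥ 20 | 43, p) reaches 80%: p = 51.8%.

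**4. Dependence on the interval, n = 43.**

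| Interval | Responders needed | Power at 50% | One-sided type I error |
|---|---|---|---|
| Exact (Clopper-Pearson) | 20 | 72.9% | 1.6% |
| Wald | 20 | 72.9% | 1.6% |
| Mid-P | 20 | 72.9% | 1.6% |
| Wilson, Agresti-Coull, Jeffreys | 19 | 82.0% | 3.4% |

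**5. Other sample sizes, exact interval.** The plan allows 20 to 60 subjects.

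| n | Responders needed | Power at 50% |
|---|---|---|
| 20 | 11 | 41.2% |
| 28 | 14 | 57.5% |
| 43 | 20 | 72.9% |
| 44 | 20 | 77.4% |
| 45 | 21 | 72.4% |
| 46 | 21 | 76.9% |
| 47 | 21 | 80.9% |
| 60 | 26 | 87.7% |

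Exact power first reaches 80% at n = 47 and stays at or above 80% for every n from 54 to 60. At n = 20 and n = 28 the thresholds of 11 and 14 are the same under the exact, Wilson, Wald and mid-P intervals.

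**The case against.** **The plan does not say Clopper-Pearson, and another exact method accepts 19.** A two-sided exact binomial test that orders outcomes by probability gives p = 0.047 at 19 of 43 and so rejects, with 82.0% power. The reading of the interval is indeed an assumption. But Clopper-Pearson is the standard meaning of an exact binomial interval, and the plan decides by the confidence limit, not by that test. The one-sided exact p-value at 19 of 43 is 0.034, above 0.025, so the equal-tailed exact interval does not exclude 30%.

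**Sizing by approximation and reporting an exact interval is ordinary practice.** That explains the figure. It does not make 80% the power of the stated rule.

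**Part of the gap is discreteness.** This is fair: one more subject raises power from 72.9% to 77.4%. The plan nevertheless makes its claim at exactly 43.

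**A Wilson interval would support the claim.** It gives 82.0%, but Wilson appears only in the amendment rationale, for a hypothetical 19 of 43 (lower limit 30.4%). Neither document's analysis section names it. That example does show that 19 of 43 is the count on which the two intervals disagree.

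**The point cannot change the trial's conclusion.** This stands. The amendment summary reports 28 enrolled and an ORR of 67.9%, that is 19 of 28, counted with pseudo-progression taken into account. The exact lower limit is 47.6%, and 28 subjects need 14 responders under each of the four intervals compared. It limits the weight of the point but does not make the stated design property correct.

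**Protocol 8.1 leaves analytic detail to the SAP.** So the protocol's looser wording is not an error in itself. Naming the exact interval there is alignment; the restated power is the substantive correction.

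**Conclusion.** The concern holds. Under the plan's own rule and interval, 43 subjects require at least 20 responders and give 72.9% power at a true ORR of 50%. That is about 7 percentage points below the stated 80%. The cause is a mismatch between the apparent sizing method and the analysis interval, not a calculation error.

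The result assumes that the exact binomial interval is the equal-tailed Clopper-Pearson interval at 95% and that the decision rests on its lower limit. The attribution of the 80% to a normal approximation is an inference.

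The discrepancy should be corrected, but its practical effect is small: the exact rule errs on the conservative side, and the reported 19 of 28 does not depend on it.

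**What to change.** **Essential, SAP 1.3.** Keep 43 as the planning figure, have the sponsor name the method that produced it, and add:

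> Under the decision rule of SAP 1.3 and protocol 8.2, using the exact binomial (Clopper-Pearson) 95% CI of SAP 5.5.1, 43 subjects need at least 20 responders and give 73% power at a true ORR of 50% (one-sided type I error 1.6%).

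Because 20 to 60 subjects are allowed, it would help to add:

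> With 20 subjects, at least 11 responders are needed (41% power); with 60 subjects, at least 26 (88% power).

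**For consistency.** Make the same statement in protocol 8.5 and the synopsis. In SAP 1.3, protocol 8.4.2 and the synopsis entry for the primary endpoint, change binomial to exact binomial so that all agree with SAP 5.5.1.

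**Cost.** These are wording changes only: no extra patients, no change to the SAP's analysis method, and no change to the 30% criterion. The stated power becomes less favourable. The protocol edits need an amendment, which protocol 11.3 sends to the ethics committee for approval or filing. They also fix as exact an interval the protocol had left as binomial, a choice SAP 5.5.1 has already made. If an amendment for wording alone is not warranted, the SAP 1.3 edit can go first.
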